[figure not shown]
[figure not shown]
[figure not shown]
[figure not shown]
[figure not shown]
[figure not shown]
[figure not shown]
Confidential

[figure not shown]
[figure not shown]
[figure not shown]
[figure not shown]
[figure not shown]
[figure not shown]
[figure not shown]
Confidential

[figure not shown]
[figure not shown]
[figure not shown]
Confidential

[figure not shown]
[figure not shown]
Confidential

[figure not shown]
[figure not shown]
[figure not shown]
Confidential

[figure not shown]
Confidential

2 Protocol Synopsis

Focal Pain Outcomes using Configurations Applied for Lateral Stimulation FOCAL	
Study Objective(s)	To evaluate Multiple Independent Current Control (MICC) perception and sub-perception based programming at Dorsal Column (DC) targets and Dorsal Root (DR) targets for focal foot, knee, or groin pain relief.
Device/System used in accordance with the Instructions For Use (IFU)	WaveWriter™ Boston Scientific Spinal Cord Stimulation systems.
Control Device applied as Standard of Care and sizes, if applicable	None; each subject will serve as their own control.
Study Design	Multi-center, double blind randomized controlled cross-over (Study design flow chart, see Error! Reference source not found.).
Planned Number of Subjects	[REDACTED]
Planned Number of Sites / Countries	[REDACTED].
Primary Endpoint	There is no primary endpoint. Collected data will be used to increase the understanding of the therapy, guide product development and help define the best practice for programming patients with focal foot, knee, or groin pain using Spinal Cord Stimulation devices.
Safety parameters	
 • Rate of device and/or procedure related non-serious adverse events • Rate of device and/or procedure related serious adverse events • Rate of unanticipated adverse device effects
Exploratory Endpoints	[REDACTED]

[figure not shown]
Focal Pain Outcomes using Configurations Applied for Lateral Stimulation	
	FOCAL
	
Method of Assigning Patients to Treatment	

Focal Pain Outcomes using Configurations Applied for Lateral Stimulation FOCAL	
Follow-up Schedule	
 • Screening/Baseline Visit • Implant (contingent on >80% coverage of pain location in OR) 
Period 1 (4 ± 1.5 weeks)
 
 • Visit 1: Perception based search • Visit 2: Perception based evaluation • Visit 3: Perception based search for opposite lead 
Washout Period (up to 7 days)
 
Period 2 (4 ± 1.5 weeks)
 
 • Call or Optional Visit: Perception based stimulation turn on • Visit 1: Perception based evaluation • Visit 2: Sub-perception based search (Randomized lead implant) 
Washout period (up to 7 days)
 
Period 3 (6 ± 2 weeks)
 
 • Call or Optional Visit: Sub-perception based stimulation turn on • Visit 1: Sub-perception based evaluation • Visit 2: Sub-perception based search for opposite lead 
Washout period (up to 7 days)
 
Period 4 visit (6 ± 2 weeks)
 
 • Call or Optional Visit: Sub-perception based stimulation turn on • Visit 1: Sub-perception based evaluation 
Long Term Follow up (12 ± 4 weeks)
 
 • Visit 1: Initial long-term follow-up visit • Call or Optional Visit: Long term follow-up evaluation • Visit 2: Final long-term follow-up visit = end of study
Study Duration	
Participant Duration	

[figure not shown]
Focal Pain Outcomes using Configurations Applied for Lateral Stimulation FOCAL	
Inclusion Criteria	
IC1. Average unilateral foot, knee, or groin pain (of neuropathic origin only) intensity of 6 or greater on a 0-10 numerical rating scale at Baseline Visit based on 7-day average NRS score
 
IC2. Subject signed a valid, EC-approved informed consent form (ICF)
 
IC3. Willing and able to comply with all protocol-required procedures and assessments/evaluations
 
IC4. [REDACTED]
 
[REDACTED]
 
[REDACTED]
 
[REDACTED]
 
[REDACTED]
 
IC7. 18 years of age or older when written informed consent is obtained

Exclusion Criteria	
EC1. Significant cognitive impairment at Screening that, in the opinion of the Investigator, would reasonably be expected to impair the study candidates to participate in the study
 
EC2. [REDACTED]
 
[REDACTED]
 
EC3. Participating (or intends to participate) in another drug or device clinical trial that may influence the data that will be collected for this study
 
EC4. [REDACTED]
 
[REDACTED]
 
[REDACTED]
 
[REDACTED]

Multiple Interventions	NA
Statistical Methods	

Focal Pain Outcomes using Configurations Applied for Lateral Stimulation FOCAL	
Primary Statistical Hypothesis	None
Statistical Test Method	Analysis of study data will include descriptive statistical methods in post-hoc analysis.
Sample Size Parameters	No power estimates were used to drive sample size calculations.

[figure not shown]
Confidential

[figure not shown]
Confidential

[figure not shown]
3 Table of Contents

[figure not shown]
[figure not shown]
Confidential

[figure not shown]
Confidential

Confidential

Confidential

4 Introduction

4.1 Chronic Intractable Pain

Chronic intractable pain is often defined as pain persisting for at least 6 months which has not responded to conservative treatment(s). The pain may be due to current or past nerve injury and can result in significant disability, reduced work productivity, reduced quality of life, and significant cost burden. Early treatments for chronic pain typically include over-the-counter and prescription medications. Later treatments like physical therapy and interventional pain procedures (e.g. intraspinal injections, vertebroplasty, pulsed RF) are attempted, sometimes followed by chronic high dose opioids and back surgery, if indicated. If back surgery is unsuccessful in relieving the chronic pain, the patient can be labeled as having failed back surgery syndrome (FBSS). Spinal cord stimulation is an option in the well-selected patient with chronic low back and/or leg pain. Such pain can lead to a number of co-morbidities, including reduced health-related quality of life, reduced ability to engage in activities of daily living, increased disability, increased emotional depression, and weight gain due to the adoption of a sedentary lifestyle. Chronic low back and/or leg pain is typically categorized as either neuropathic, which involves pathological nerve activity and is commonly characterized by patients as ‘shooting’ or ‘burning’; nociceptive, which involves nerve signals indicating actual or impending tissue damage or inflammation (Grbois et al., 2005); or a varying mixture of neuropathic and nociceptive pain.

4.2 Conventional Spinal Cord Stimulation

SCS is effective for chronic intractable pain associated with a variety of conditions, including, but not limited to: FBSS (Carter et al., 2004, Taylor et al., 2004), complex regional pain syndrome (Sears et al., 2011), low back pain and leg pain (Cameron et al., 2004). Spinal cord stimulation (SCS) is a less invasive treatment option for FBSS but has generally been reserved for patients who have failed multiple, and indeed all possible, repeat operations. With SCS, an implanted pulse generator (IPG) delivers electrical current to electrode(s) implanted in the epidural space. This electrical current causes activation of nerves and can be programmed to direct stimulation to the nerves innervating the painful location, resulting in a reduction of the intensity of that pain (Kumar et al., 2006). Before an SCS system is implanted, a patient often undergoes a screening trial with an electrode that is connected to an external stimulator that the patient wears outside of the body. The results of the screening trial can predict the patient’s outcome with an implanted system (Kumar et al., 2006).

In SCS pain relief is realized when the nerves that innervate the painful region(s) are electrically stimulated (North et al., 1990). To increase the chance of success, the electrode contacts are programmed based on the patient feedback about location of the stimulation induced paresthesia in response to various combinations of contact polarities (anodes and cathodes), pulse rate (or frequency), pulse amplitude (or current), and pulse width.

In an international multi-center RCT, Kumar et al (2007) randomized 100 patients: 48 subjects to conventional medical management alone (CMM group) and 52 subjects to SCS plus CMM (SCS group). At 6 months, patients randomized to SCS achieved significantly greater pain relief and improved functional capacity and health-related quality of life compared with patients randomized to CMM. Specifically, twenty four patients in the SCS group (48%) and four

patients in the CMM group (9%) achieved the primary outcome of 50% leg pain relief ($p < 0.001$) at 6 months. This trend continued over the duration of 12 months as reported in Kumar 2007 with the SCS group experiencing improved pain relief, quality of life and functional capacity, as well as greater treatment satisfaction ($p \leq 0.05$). At 24 months (Kumar 2008), 37% of patients in SCS group continued to achieve at least 50% pain relief versus 2% of patients in the CMM group ($p = 0.003$). The results from the PROCESS study provide evidence that SCS is effective and cost effective in relieving chronic neuropathic pain associated with FBSS.

4.3 Sub-perception Electrical Stimulation

Traditionally, SCS has relied on the understanding that to achieve pain relief, dorsal column stimulation-induced paresthesia has to be generated overlying the area of pain in order to successfully treat pain (North et al. 1991). However, recent studies indicate that effective pain relief may be obtained by employing stimulation without paresthesia.

Van Buyten et al. (Van Buyten et al. 2012) reported the outcomes of a prospective, open-label, multicenter European clinical trial that utilized high frequency (up to 10 KHz) which did not produce paresthesia. Of 82 patients, 72 reported a significant improvement in VAS scores after trial and underwent permanent implantation. At six months, 74% of patients had a greater than 50% pain relief in back pain. Al-Kaisy et al. (Al-Kaisy et al., 2014) reported the long term outcomes of this cohort at 24 months – Mean back pain was reduced from 8.4 ± 0.1 at baseline to 3.3 ± 0.3 at 24 months ($p < 0.001$), and mean leg pain was reduced from 5.4 ± 0.4 to 2.3 ± 0.3 ($p < 0.001$). At 24 months, 60% of implanted patients had a greater than 50% pain relief in back pain.

Thomson et al. (Thomson et al., 2018) reported outcomes of a multicenter, double-blind, crossover, randomized controlled trial (PROCO) that investigated the effects of rate on analgesia in kilohertz frequency (1–10 kHz) spinal cord stimulation (SCS). The sweet spot identified at 10 kHz in all patients was tested at 1, 4, 7, and 10 kHz SCS in randomized order (four weeks at each frequency). With appropriate titration of pulse width and amplitude, all frequencies resulted in equivalent pain relief ($p \leq 0.002$). The charge was not constant across all frequencies and 1 kHz stimulation required significantly less charge than higher frequencies.

DeRidder et al. (DeRidder et al 2010) reported the outcomes of a new stimulation paradigm (burst) used in 12 patients without paresthesia induction. During the trial period, an improvement of 5.25 points on VAS for axial pain for burst stimulation ($p < 0.001$) was reported versus a 1.83 points improvement for tonic stimulation. After more than 1 yr. of follow up, significant reduction in VAS scores for axial pain of 3.7 points and for limb pain of 5.15 points was noted with burst stimulation.

4.4 Lateral nerve root stimulation for focal pain

Lateral stimulation, leads placed laterally in the epidural space to target roots has been previously reported (Palmeri et al., 2012 and Sharan et al., 2008). MacDougall et al. has recently published outcomes in an open label, single site, prospective study (MacDougall et al., 2017) using lateral stimulation to target nerve roots. In the patients that received laterally implanted leads targeting DNR (dorsal nerve root), there was a VAS score decrease from 7.5 (SD 1.4) to

4.4 (SD 2.6). Forty seven percent of patients with permanent DNR stimulation implants achieved at least 50% pain relief. [name] has published outcomes (Pyles et al., 2017) using lateral stimulation to target foot pain. Leads were placed antegrade through the sacral hiatus within a range of L5 - S1. The average decrease in pain was 6.3 across 9 patients. Both standard stimulation parameters and higher rates were tested. At the final follow up, 55.6% of patients were using standard based programs and 44.4% of patients were using higher rates.

4.5 Optimized lateral nerve root stimulation for focal foot, knee, or groin pain

Outcomes reported by Drs. Parrent, MacDougall, and Pyles, have shown lateral stimulation to be effective for targeting focal pain with a single lead implanted on each side. Paddle leads with multiple columns have also been used to target roots (data not published).

The purpose of this study is to explore spatial sensitivity and frequency sensitivity in sub-perception in lateral nerve root stimulation to obtain initial impressions of effects.

5 Device Description (used in accordance with the IFU)

6 Study Objectives and Endpoints

The objective of this study is to evaluate MICC perception and sub-perception based programming at DC and DR targets for focal pain relief.

The following Safety parameters will be collected in the study:

- Rate of device and/or procedure related non-serious adverse events
- Rate of device and/or procedure related serious adverse events

7 Study Design

*: Randomization

Post-implant

Confidential

[figure not shown]
[figure not shown]
Figure 7-1: FOCAL Main-Study Design Flowchart

Confidential

[figure not shown]

8 Surgical Methodology

Subjects with a history of unilateral neuropathic foot, knee, or groin pain will be enrolled.

[figure not shown]
9 Study Design

9.2.1 Treatment and Control

This study compares two stimulation implant locations, DC and DR, with both perception based and sub-perception types of stimulation. The cross-over study design allows for comparing these treatments using one of the stimulation types as an active control.

9.3 Justification for the Study Design

[REDACTED]

[REDACTED]

[REDACTED]

[REDACTED]

10.2 Inclusion Criteria

Subjects who meet all of the following criteria (see Table 10.2-1) may be given consideration for inclusion in this clinical investigation, provided no exclusion criterion (see Section 10.3) is met.

Table 10.2-1: Inclusion Criteria

Inclusion Criteria	IC1. Average unilateral foot, knee, or groin pain (of neuropathic origin only) intensity of 6 or greater on a 0-10 numerical rating scale at Baseline Visit based on 7-day average NRS score IC2. Subject signed a valid, EC-approved informed consent form (ICF) IC3. Willing and able to comply with all protocol-required procedures and assessments/evaluations IC4. [REDACTED] [REDACTED] [REDACTED] [REDACTED] IC7. 18 years of age or older when written informed consent is obtained
---------------------------	---

10.3 Exclusion Criteria

Subjects who meet any one of the following criteria (Table 10.3-1) cannot be included in this study or will be excluded from this clinical study.

Table 10.3-1: Exclusion Criteria

Exclusion Criteria	
EC1. Significant cognitive impairment at Screening that, in the opinion of the Investigator, would reasonably be expected to impair the study candidates to participate in the study
 
EC2. [REDACTED]
 
EC3. Participating (or intends to participate) in another drug or device clinical trial that may influence the data that will be collected for this study
 
EC4. [REDACTED]
 
[REDACTED]
 
[REDACTED]
 
[REDACTED]

---------------------------	--

11 Subject Accountability

11.1 Point of Enrollment

A subject will be considered enrolled in this study after he/she signs and dates the informed consent form (ICF). No study-related procedures or assessments can take place until the informed consent form is signed. Patients with a failure to find the Sweet Spot (paresthesia overlap with pain) at neither the DC nor the DR leads during OR testing will be withdrawn from the study. All applicable case report forms (CRFs) up to the point of subject withdrawal and an “End of Study” form must be completed. Additional data may no longer be collected after the point at which a subject has been withdrawn from the study. Data collected up to the point of subject withdrawal may be used and analyzed. These patients will not be count towards the enrollment ceiling.

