11.2 Withdrawal

All subjects enrolled in the clinical study (including those withdrawn from the clinical study or lost to follow-up) shall be accounted for and documented. If a subject withdraws from the clinical investigation, the reason(s) shall be reported. If such withdrawal is due to problems related to investigational device safety or performance, the investigator shall ask for the subject’s permission to follow his/her status/condition outside of the clinical study.

Reasons for withdrawal could include but are not limited to:

Physician discretion

- Subject's choice to withdraw consent;
- Subject's failure to meet inclusion or not meet exclusion criteria after enrollment but prior to first study related programming
- Failure to find the Sweet Spot (paresthesia overlap with pain) at neither the DC nor DR leads during OR testing
- Subject is lost to follow-up or
- Subject's death

While study withdrawal is discouraged, subjects may withdraw from the study at any time, with or without reason, and without prejudice to further treatment.

All applicable case report forms (CRFs) up to the point of subject withdrawal and an "End of Study" form must be completed. Any subject deemed "lost to follow-up" should have a minimum of three documented attempts to contact him/her prior to completion of the "End of Study" form.

Additional data may no longer be collected after the point at which a subject has been withdrawn from the study or withdraws consent, for whatever reason. All open adverse events should be closed or documented as unresolved. Data collected up to the point of subject withdrawal may be used and analyzed.

Withdrawn subjects will not be included in the site's overall total for subjects.

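### Data collection stops at any withdrawal, so related adverse events that first appear after an OR-testing or physician-discretion withdrawal may not enter the safety rates, and the end of event reporting is worded inconsistently

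*Combined protocol and SAP*

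**What the plan says.** **Who is withdrawn.** Under Section 11.1, patients with no Sweet Spot "at neither the DC nor the DR leads during OR testing will be withdrawn from the study". Section 11.2 repeats this reason. It also lists "Physician discretion", the subject's own withdrawal of consent, loss to follow-up, death, and failure against the eligibility "criteria after enrollment but prior to first study related programming".

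**What stops.** Section 11.1, directly after the Sweet Spot provision: "Additional data may no longer be collected after the point at which a subject has been withdrawn from the study". Section 11.2 repeats the bar for a subject who is "withdrawn from the study or withdraws consent, for whatever reason". The last three of those words stand only in 11.2.

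**What is kept.** "Data collected up to the point of subject withdrawal may be used and analyzed". Section 11.2 asks that events still open at withdrawal be closed or marked unresolved. It also requires all enrolled subjects to be accounted for, "including those withdrawn from the clinical study or lost to follow-up".

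**What follow-up remains.** Where the withdrawal stems from device safety or performance problems, 11.2 tells the investigator to ask permission to follow the subject, outside the study. Sections 12.3.1 and 12.15 return subjects to the center's routine care.

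**When reporting ends.** Table 19.4-1 runs reporting to the end of the study, which 11.4 defines by the last scheduled visit or procedure in the trial. The text below the table runs it, per subject, to the end of participation, which 12.15 places at withdrawal if that comes first.

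**What the data feed.** The Synopsis and Section 6 list as safety parameters the rates of serious and non-serious events related to the device or procedure.

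**The concern.** Stopping collection is natural when a subject revokes consent. Here the same stop covers withdrawals that the subject did not request, including one that the protocol itself imposes during the lead procedure. Some procedure-related events may appear only later. If such an event arises after the subject has been withdrawn, a site that follows 11.1 and 11.2 has no visible instruction to enter it in the study data.

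This bears on the safety parameters, which are among the few outcomes that can be read in the public text. Section 18.2 acknowledges added risk from placing up to 2 electrodes at a lower spinal level, and from implanting up to 4 electrodes where 2 is standard. Subjects withdrawn at OR testing have been exposed to at least part of that procedure.

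**Working it through.** The plan states no figure that can be reproduced here, so the check is mainly a comparison of passages.

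**Step 1. Which withdrawals does the stop reach?**

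| Reason (11.1, 11.2) | Subject's own request? | Lead procedure already begun? | In-study recording of new events afterwards |
|---|---|---|---|
| No Sweet Spot at OR testing | No | Yes: the leads are being tested | None visible |
| Physician discretion | No | Possible: no time limit is stated | None visible |
| Eligibility failure before first programming | No | Not established (see objection) | None visible |
| Consent withdrawn | Yes | Possible | None, as expected |

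The point rests on the first two rows.

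**Step 2. When does reporting end?**

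| Source | Completer | Withdrawn subject |
|---|---|---|
| 11.1 and 11.2 | Not applicable | Withdrawal |
| Text below Table 19.4-1, with 12.15 | End of Study Visit | Withdrawal |
| Table 19.4-1, with 11.4 | Last scheduled visit or procedure | Last scheduled visit or procedure in the trial |

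For completers the end points largely coincide. For withdrawn subjects the last row differs from the other two.

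**Step 3. How much recording time is involved?** Inputs are from the Synopsis follow-up schedule: Periods 1 and 2 at 4 ± 1.5 weeks each, Periods 3 and 4 at 6 ± 2 weeks each, long-term follow-up at 12 ± 4 weeks, and three washouts of up to 7 days.

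- Full schedule: 4 + 4 + 6 + 6 + 12 = 32 weeks. Tolerances: 1.5 + 1.5 + 2 + 2 + 4 = 11, giving 21 to 43. Full washouts add 3, so the maximum is 46.
- Left after Period 1: 4 + 6 + 6 + 12 = 28. Minimum 28 − 9.5 = 18.5; maximum 28 + 9.5 + 3 = 40.5.
- Left after Period 2: 6 + 6 + 12 = 24. Minimum 24 − 8 = 16; maximum 24 + 8 + 2 = 34.
- Left after Period 3: 6 + 12 = 18. Minimum 18 − 6 = 12; maximum 18 + 6 + 1 = 25.
- Left after Period 4: 12, range 8 to 16.

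These figures only restate the remaining schedule for an implanted subject. The interval from implant to Period 1 is not visible and is not counted. The 32 weeks are not a fair comparator for OR failures, because the Synopsis makes implantation conditional on pain coverage in the OR. An OR failure has no recorded time after the procedure only if withdrawal takes effect at testing, and the visible text does not settle that.

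**Step 4. Can an effect on the rates be derived?** No. No withdrawal, OR-failure or event rate is visible. The direction also depends on the denominator. If withdrawn subjects stay in it while their later events are missing, a subject-level rate can only be lowered or unchanged. If they are left out altogether, the rate becomes that of the remaining subjects, which may be higher or lower. The visible part of 13.2.1 names intent-to-treat and per-protocol analyses but no safety set. Section 11.2 adds "Withdrawn subjects will not be included in the site" (the sentence goes on to the site's overall total), which reads as an enrollment count and does not settle the denominator.

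**The case against.** **The reporting passages can be read together.** The Synopsis calls the subject's final long-term visit the end of study, and 11.1 and 11.2 require an End of Study form at withdrawal. If the table's end point is taken per subject, 11.1, 11.2, 12.15 and 19.4 agree. Only the trial-level wording of 11.4 stands against this. The objection holds to that extent: this is inconsistent wording more than two rival instructions. It does not remove the main point, because the passages would then agree on a stop at withdrawal.

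**Section 19.1.** A reader might infer that it contradicts 11.2, because it requires events after the procedure to be recorded. It gives no end date, however, and recording up to withdrawal satisfies it.

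**Consent.** A reader might infer that consent still stands after a withdrawal that the subject did not request. The consent form is not visible, so this cannot be checked.

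**Eligibility failures after implant.** A reader might infer these, since the first programming search follows implant in the schedule. The visible criteria that carry a time point are tied to Screening, Baseline or consent, and others are redacted. The inference is not secure.

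**A safety route exists.** The permission-based follow-up in 11.2 is real and deserves weight. On its face it does not cover a failed Sweet Spot search or physician discretion as such, and what it yields lies outside the study.

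**Hidden text.** Section 12.5 has no visible content and 12.6 to 12.14 are not shown. Post-procedure handling of OR failures could be described there.

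**Conclusion.** The concern holds in limited form and is minor. As the visible text stands, a related event that first appears after an OR-testing or physician-discretion withdrawal may not enter the safety rates, and the reporting end point for withdrawn subjects is worded inconsistently. This assumes that no redacted section and no consent wording already provides in-study safety recording for these subjects.

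The documents do not support a claim that the rates will be biased by a given amount or in a given direction. Nor do they support a claim that withdrawn subjects disappear from the data, since their data up to withdrawal remain usable and open events keep a recorded status. They also do not suggest that these subjects go without care. The unstated denominator is a secondary gap. The study has no primary endpoint and no hypothesis, its analysis is descriptive, and no visible decision threshold rests on these rates, so no main result is threatened.

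**What to change.** - In 11.1 and 11.2, separate withdrawal of consent from withdrawal initiated by the protocol or the investigator. For the latter, as far as the consent form allows (amended if needed), keep recording device- or procedure-related events and all serious events for a stated period in subjects in whom lead placement was started. Take the information from the routine care that 12.3.1 and 12.15 already describe.
- Reconcile 11.1, 11.2, 11.4, 12.15 and 19.4 on one end point for event reporting, stated separately for completers, subjects who withdraw consent, and other withdrawals.
- In Section 13, report the safety rates over all subjects in whom lead placement was started, with OR failures on a separate line.

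The cost is protocol and consent wording and a few more adverse event entries, with no extra study visits.
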